9.3.2 Clinical Events Committee (CEC)

An independent CEC will be established to review and adjudicate each suspected bleeding event, MACE (CV death, non-fatal MI, non-fatal stroke, recurrent ischemia with hospitalization, urgent coronary revascularization) and probable/definite stent thrombosis identified by investigators or triggered by predefined criteria with the appropriate supporting documentation for the event. The group will use the definitions of the endpoints of the protocol (**Appendix B**) and additional instructions for its interpretation so that the adjudication proceeds in consistent fashion overtime. The CEC will comprise physician personnel (interventional cardiologists) who are not investigators in the study and not otherwise directly associated with the sponsor. The CEC judges will remain blinded to treatment throughout the adjudication process and the study. The CEC-adjudicated data will

be used in the final analyses of certain endpoints. The CEC will be described in detail in a separate CEC Charter.

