Cardiovascular death is the endpoint defined in this trial (as opposed to all-cause death) and only suspected CV death cases will be submitted for adjudication to the CEC. Death will be classified as cardiovascular, non-cardiovascular, or unknown/undetermined. All deaths will be assumed to be cardiovascular in nature unless a non-cardiovascular cause can be clearly shown, with the exception of death without any additional information, which will be classified as unknown/undetermined.

The primary cause of death is determined by the principal condition that caused the death, not the immediate mode of death, as per the following:

Cardiovascular death:

- **Acute MI**

Death by any cardiovascular mechanism (arrhythmia, sudden death, HF, stroke, pulmonary embolus, PAD) within 30 days after an acute MI, related to the immediate consequences of the MI, such as progressive HF or recalcitrant arrhythmia. There may be assessable (attributable) mechanisms of cardiovascular death during this time period, but for simplicity, if the cardiovascular death occurs within 30 d of an acute MI, it will be considered a death due to MI.

Note: Acute MI should be verified to the extent possible by the diagnostic criteria outlined for acute MI or by autopsy findings showing recent MI or recent coronary thrombosis. Death resulting from a procedure to treat an MI (PCI or CABG), or to treat a complication resulting from an elective coronary procedure to treat myocardial ischemia (i.e., chronic stable angina) or death due to an MI that occurs as a direct consequence of a cardiovascular investigation/procedure/operation should be considered as a death due to a cardiovascular procedure.

- **Sudden cardiac death**

Death that occurs unexpectedly and not within 30 d of an acute MI.

Note: Sudden cardiac death includes the following scenarios:

- Death witnessed and occurring without new or worsening symptoms;
- Death witnessed within 60 min of the onset of new or worsening cardiac symptoms unless the symptoms suggest acute MI;
- Death witnessed and attributed to an identified arrhythmia (e.g., captured on an ECG recording, witnessed on a monitor, or unwitnessed but found on ICD review);
- Death after unsuccessful resuscitation from cardiac arrest (e.g., ICD unresponsive sudden cardiac death, pulseless electrical activity arrest);
- Death after successful resuscitation from cardiac arrest and without identification of a specific cardiac or noncardiac etiology;

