-Unwitnessed death in a subject seen alive and clinically stable ≤ 24 h before being found dead without any evidence supporting a specific non-cardiovascular cause of death (information about the subject's clinical status preceding death should be provided if available)

Unless additional information suggests an alternate specific cause of death (e.g., death due to Other cardiovascular causes), if a subject is seen alive ≤ 24 h before being found dead, sudden cardiac death should be recorded (e.g., subject found dead in bed but who had not been seen by a family member for >24 h).

- Death due to heart failure

Death associated with clinically worsening symptoms and/or signs of HF, regardless of etiology.

Note: Deaths due to HF can have various etiologies, including single or recurrent MIs, ischemic or nonischemic cardiomyopathy, hypertension, or valvular disease.

- Death due to stroke

Death after stroke that is either a direct consequence of the stroke or a complication of the stroke.

Note: Acute stroke should be verified to the extent possible by the diagnostic criteria outlined for stroke.

- Death due to cardiovascular procedures

Death caused by the immediate complication(s) of a cardiovascular procedure.

- Death due to cardiovascular hemorrhage

Death related to hemorrhage such as a nonstroke intracranial hemorrhage (e.g., subdural hematoma), nonprocedural or nontraumatic vascular rupture (e.g., aortic aneurysm), or hemorrhage causing cardiac tamponade.

- Death due to other cardiovascular causes

Cardiovascular death not included in the above categories but with specific, known cause (e.g., PE, PAD).

Non-cardiovascular death: defined as any death with a specific cause that is not thought to be cardiovascular in nature:

- Pulmonary
- Renal
- GI
- Hepatobiliary
- Pancreatic
- Infection (includes sepsis)
- Inflammatory/immune (includes SIRS, immunological, autoimmune diseases and disorders, anaphylaxis from environmental allergies)
- Hemorrhage that is neither cardiovascular bleeding nor a stroke
- Non-cardiovascular procedure or surgery

- Trauma (includes homicide)
- Suicide
- Prescription drug reaction or overdose (includes anaphylaxis)
- Nonprescription drug reaction or overdose
- Neurological (excludes cardiovascular death from ischemic stroke, hemorrhagic stroke, or undetermined cause of stroke, or cardiovascular hemorrhage of central nervous system)
- Malignancy
- Other non-cardiovascular cause of death

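### The example attached to the 24-hour rule for sudden cardiac death does not meet that rule, so an unseen death with no further information has two conflicting classifications

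*Combined protocol and SAP*

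**What the plan says.** Appendix B, under Death, opens with a general rule: "All deaths will be assumed to be cardiovascular in nature unless a non-cardiovascular cause can be clearly shown". The same sentence carves out one case, "with the exception of death without any additional information, which will be classified as unknown/undetermined".

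Under Sudden cardiac death, a subtype of cardiovascular death, a note begins "Sudden cardiac death includes the following scenarios". The last scenario listed is "Unwitnessed death in a subject seen alive and clinically stable ≤ 24 h before being found dead", provided that no evidence supports a specific non-cardiovascular cause. A closing sentence repeats the time limit as an instruction: unless other information points to a different specific cause, "if a subject is seen alive ≤ 24 h before being found dead, sudden cardiac death should be recorded". The parenthesis that ends this instruction is its only example: "e.g., subject found dead in bed but who had not been seen by a family member for >24 h".

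Section 9.3.2 says of the CEC that "The group will use the definitions of the endpoints of the protocol", together with further instructions on how to interpret them. Under Section 7.6, only CEC-adjudicated events enter the secondary efficacy analyses. Section 7.6.1 lists cardiovascular death both as a component of MACE and as an outcome in its own right, through 30 and 90 days.

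**The concern.** An example normally shows a rule being met. This one describes a subject who, on the ordinary reading, fails the rule. An adjudicator with such a case can follow the stated time limit, which does not cover it, or the example, which says to record sudden cardiac death. No sentence in Appendix B addresses a subject last seen more than 24 h earlier, so the reader has to fall back on the general rule for deaths, and that rule can give a different answer from the example.

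At stake is whether a death found late counts as cardiovascular, and so as MACE. The situation is plausible in this trial. After discharge, scheduled contact is one visit at 14 days and telephone calls at 30 and 90 days, so a death at home may go unobserved. Appendix B also sends only suspected cardiovascular deaths to the CEC, so a site may meet the ambiguity before central review does.

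**Working it through.** No arithmetic applies. The plan states no figure on this point, and the check is whether the texts agree.

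**Step 1: condition against example.** The condition is that the time since the subject was last seen alive is at most 24 h. It appears twice, once in the list of scenarios and once in the recording instruction. The example has more than 24 h since a family member saw the subject. It meets the condition only if someone outside the family saw the subject within 24 h, and the text does not say so.

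**Step 2: does the condition exclude the example?** No. The scenario list is introduced by a word that leaves it open, and nothing says that a subject unseen for longer cannot be a sudden cardiac death. The 24-hour sentence is silent on that subject.

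**Step 3: what each text gives for a subject unseen for more than 24 h.**

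| What else is known | Example | 24-hour condition | General rule for deaths | Does the endpoint differ? |
|---|---|---|---|---|
| A non-cardiovascular cause is clearly shown | Does not apply, because the instruction yields to another specific cause | Silent | Non-cardiovascular | No |
| Some information, but no non-cardiovascular cause clearly shown | Sudden cardiac death, hence cardiovascular; if another cause is only suggested, the instruction drops out and the general rule decides | Silent | Cardiovascular, by presumption | No |
| No additional information at all | Sudden cardiac death, hence cardiovascular and MACE | Silent | Unknown/undetermined, not MACE | **Yes** |

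**Step 4: where the conflict lies.** Only the last row changes an endpoint. In the middle row the subtype may be open, but the analysed outcome is cardiovascular death, and that is the same under either text.

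**The case against.** Several points limit the concern, and most of them stand.

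- **The rule does not bar the case.** A reader might infer that the CEC is told to count a death that the rule excludes. The documents do not support this: the list of scenarios is open-ended, so the case is uncovered, not forbidden.
- **Most late-found deaths are unaffected.** A reader might infer that every death unseen for more than 24 h turns on whether the adjudicator follows the rule or the example. The presumption of cardiovascular cause settles all of them except those with no additional information. Enrolled subjects have a recorded cardiac history, an index procedure and follow-up contacts, so that remainder may be very small.
- **The effect cannot be sized.** The documents give neither a death rate for this trial nor the share of deaths found late. Any count would rest on assumed rates, and a count of all deaths found late would measure the wrong group.
- **The CEC has other guidance.** Section 9.3.2 allows interpretive instructions, and Sections 6.6.1 and 6.7 refer to a charter that is not among the documents. It may already settle the matter. That does not repair the protocol text on which the charter is to build.
- **No formal inference depends on it.** The primary endpoint is bleeding. Section 7.6.2 treats the efficacy analyses as descriptive and the trial as too small for clinical event rates. Adjudication is blinded, so there is no reason to expect the ambiguity to favour an arm.
- **A witness outside the family could reconcile the text.** This is possible but strained, since an example that needs an unstated fact to fit its rule gives no usable guidance.
- **The origin of the slip is unknown.** The source definitions are not available, so it cannot be shown whether the example or the threshold was transcribed wrongly. This is a reason to resolve the conflict through the general rule already in Appendix B, and not through a new rule.

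**Conclusion.** The point holds in a limited form. The example contradicts the condition it illustrates, in current endpoint-definition text that the CEC is told to apply. The consequence is confined to deaths unseen for more than 24 h and without any additional information: the example makes them cardiovascular deaths and MACE events, and the general rule makes them unknown/undetermined. All other late-found deaths receive the same endpoint classification under either text. Few deaths should be affected, and no numerical size is claimed.

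This conclusion assumes the ordinary reading of the example, that is, that nobody is known to have seen the subject within 24 h. It also assumes that the charter does not already resolve the case. It concerns a descriptive secondary outcome and does not bear on the bleeding comparison. It is a minor correction, worth making because it removes discretion over an outcome for which few events are likely.

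**What to change.** Remove the parenthetical example from the 24-hour sentence in Appendix B. Then add one sentence, there and in the CEC charter, saying that a subject not seen alive within 24 h of being found dead is classified by the general rule for deaths: cardiovascular by default, non-cardiovascular only on clear evidence, and unknown/undetermined only when there is no additional information. The sentence should keep that last restriction explicit, so that adjudicators do not code every late-found death as unknown and so weaken the presumption. If the sponsor intended the example to stand, the time limit and the exception in the general rule would both have to be reworded to agree with it.

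Optionally, show unknown/undetermined deaths by arm beside cardiovascular deaths. Section 7.5.4 already plans a listing of all deaths, so this is a matter of presentation.

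The cost is one sentence in each of two documents and, if wanted, one table line. Compared with following the example, the cardiovascular-death count could be slightly lower.

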APPENDIX C: ADDITIONAL SAFETY INFORMATION

A Guide to Interpreting the Causality Question

The following factors should be considered when deciding if there is a “reasonable possibility” (i.e., “possibly” or “probably”) that an AE may have been caused by the drug.

- Time Course. Exposure to suspect drug. Has the subject actually received the suspect drug? Did the AE occur in a reasonable temporal relationship to the administration of the suspect drug?
- Consistency with known drug profile. Was the AE consistent with the previous knowledge of the suspect drug (pharmacology and toxicology) or drugs of the same pharmacological class? OR could the AE be anticipated from its pharmacological properties?
- Dechallenge experience. Did the AE resolve or improve on stopping the suspect drug?
- No alternative cause. The AE cannot be reasonably explained by another etiology such as the underlying disease, other drugs, other host or environmental factors.
- Rechallenge experience. Did the AE reoccur if the suspected drug was reintroduced after having been stopped?
- Laboratory tests. A specific laboratory investigation (if performed) has confirmed the relationship?

A “reasonable possibility” could be considered to exist for an AE where one or more of these factors exist.

In contrast, there would not be a “reasonable possibility” of causality if none of the above criteria apply or where there is evidence of exposure and a reasonable time course but any dechallenge (if performed) is negative or ambiguous or there is another more likely cause of the AE.

In difficult cases, other factors could be considered such as:

- Is this a recognized feature of overdose of the drug?
- Is there a known mechanism?

Ambiguous cases should be considered as being a “reasonable possibility” of a causal relationship unless further evidence becomes available to refute this.

Causal relationship in cases where the disease under study has deteriorated due to lack of effect should be classified as no reasonable possibility.

**National Institute of Allergy and Infectious Disease and Food Allergy and Anaphylaxis
Network criteria for anaphylaxis [48]**

Anaphylaxis is highly likely when any one of the following 3 criteria are fulfilled:

1. Acute onset of an illness (minutes to several hours) with involvement of the skin, mucosal tissue, or both (e.g., generalized hives, pruritus or flushing, swollen lips-tongue-uvula)

AND AT LEAST ONE OF THE FOLLOWING

- a. Respiratory compromise (e.g., dyspnea, wheeze-bronchospasm, stridor, reduced PEF, hypoxemia)
 - b. Reduced BP or associated symptoms of end-organ dysfunction (e.g., hypotonia [collapse], syncope, incontinence)
2. Two or more of the following that occur rapidly after exposure to a *likely* stimuli for that subject (minutes to several hours):
 - a. Involvement of the skin-mucosal tissue (e.g., generalized hives, itch-flush, swollen lips-tongue-uvula)
 - b. Respiratory compromise (e.g., dyspnea, wheeze-bronchospasm, stridor, reduced PEF, hypoxemia)
 - c. Reduced BP or associated symptoms (e.g., hypotonia [collapse], syncope, incontinence)
 - d. Persistent gastrointestinal symptoms (e.g., crampy abdominal pain, vomiting)
 3. Reduced BP after exposure to *known* stimuli for that subject (minutes to several hours):
 - a. Infants and children: low systolic BP (age specific) or greater than 30% decrease in systolic BP
 - b. Adults: systolic BP of less than 90 mm Hg or greater than 30% decrease from that person's baseline

PEF, Peak expiratory flow; *BP*, blood pressure.

Modified from Sampson et al., 2006

APPENDIX D: GENERAL REQUIREMENTS FOR CLINICAL TRIALS

1 General Requirements for Clinical Trials

Sponsor (which includes its affiliates/partners) and the investigator agree to conduct the trial as described in the protocol, according to applicable laws, regulations, and principles of good clinical practice. It is the intention that the trial be conducted according to practices that will satisfy worldwide registration requirements. Therefore, in addition to satisfying locally relevant requirements for the conduct of the trial, there may be a need to satisfy other requirements, as specified in this protocol. These additional requirements may follow laws, regulations, and practices of health authorities and/or sponsor policies. While health authorities may not directly oversee the conduct of the trial, they may be recipients of marketing applications that contain the report of the trial. Sponsor will take into account the appropriateness of the trial site and facilities and be assured of the investigator's qualifications and availability for the entire duration of the trial. The investigator will ensure that there are sufficient time, staff and facilities available for the duration of the trial.

Both sponsor (represented by the "sponsor representative") and the investigator must sign the protocol (and subsequent versions of the protocol if amended) as an agreement of the details of the clinical trial. The agreement will include the acceptance of procedures for source document verification, data collection, monitoring, audit, inspection, and quality assurance. Any amendments to the protocol or changes to any trial documents must have the agreement of sponsor, the investigator, and when appropriate, the Institutional Review Board (IRB) before the amendment or change is implemented; any such agreement must be documented in writing.

It is the responsibility of the investigator to ensure that all staff personnel who will be handling, packaging, and/or shipping clinical specimens or any other hazardous or dangerous goods act in conformance with International Air Transport Association (IATA) regulations relating to the handling and shipping of hazardous or dangerous goods.

2 Monitoring and Inspections

The sponsor representative and regulatory authority inspectors are responsible for contacting and visiting the investigator for the purpose of inspecting the facilities and, upon request, inspecting the various records of the clinical study (e.g., eCRFs and other pertinent data) provided that subject confidentiality is respected.

The sponsor-appointed, study monitor is responsible for verifying the eCRFs at regular intervals throughout the study to verify adherence to the protocol-completeness, accuracy and consistency of the data- and adherence to local regulations on the conduct of clinical research. The monitor should have access to subject medical records, source documents and other study-related records needed to verify the entries on the eCRFs.

The investigator agrees to cooperate with the monitor to ensure that any problems detected in the course of these monitoring visits, including delays in completing eCRFs, are resolved. It is essential that the investigator and designated staff set aside a sufficient amount of time for these study monitoring visits to permit an adequate review of the trial's progress and study data.

This study may be selected for audit by the sponsor or inspection by regulatory authorities (e.g., FDA, DHHS, NHLBI/NIH). Inspection of site facilities (e.g., pharmacy, drug storage areas, treatment areas, laboratories) and review of original study-related records will occur to evaluate the study conduct and compliance with the protocol and applicable regulatory requirements.

3 Recording Subjects' Data

The investigator must conduct the trial and maintain records and data during and after the term or early termination of the trial in compliance with all applicable legal and regulatory requirements, including any applicable requirements of the USA Code of Federal Regulations and specific local regulations, and in accordance with ICH.

The investigator is to provide such subject data on completed Case Report Forms (CRFs) or via computer entry on an Electronic Data Capture (EDC) system. The investigator must maintain a separate subject list containing the name and address for each participant so that all can quickly be contacted by the investigator, if necessary.

Case Report Forms are an integral part of the trial and subsequent reports. They need not be completed by the investigator, but all entries are the responsibility of the investigator. The investigator is expected to review subject data before attesting in writing to the accuracy and completeness (and legibility when paper CRFs are used) of the information contained therein.

Any records or documents used as the source of information in the CRF are to be maintained and readily available for review by authorized representatives of the sponsor or regulatory agency. These records or documents are called the subject source data. These include but are not limited to hospital records, clinical and office charts, laboratory and pharmacy records, diaries, microfiches, and radiographs and correspondence.

Completed paper CRFs are to be collected by the study monitor after source document verification has been completed. Paper and electronic CRFs and the electronic database shall be the exclusive property of sponsor.

3.A Paper Case Report Forms

All paper CRFs are to be filled out using a black ball-point pen. Errors should be lined out but not obliterated and the correction inserted, initialed and dated.

3.B Electronic Data Capture (EDC)

Data collection and data management will be performed using the Medidata Rave® EDC System, developed by Medidata Solutions, Inc. Medidata Rave® is an internet-based system that enables subject randomization, data collection through electronic CRFs, review of data through automated and manual data edit checks, and online source document verification. Electronic CRFs (eCRFs) are used in place of paper CRFs, for the transcription of source document data.

3.Bi Third Party Housing

The Medidata Rave® application and the eCRF data for the clinical trial is installed and stored on a server in a central, secure facility where systems administration and backups can be performed regularly. The central facility where the server is located is neither owned nor operated by Tufts Medical Center. The data-hosting facility utilizes card-key access and video surveillance. Redundant power supply, raised floors, disaster proofing, bulletproof glass/walls, motion detection, and servers inside locked cages are all security features. Data stored at the hosting facility is backed-up and stored at an offsite location on a frequent basis.

3.Bii Authentication

Each user of the system accesses the central application through a standard web browser (e.g., Internet Explorer). At the beginning of each session, user authentication is performed through a unique and confidential combination of User identification (user ID) and password. Activities in the Medidata Rave® System are time, date, and user stamped in the database, along with duration of the sessions. After login, the system establishes a user session, so that all data recorded by the user is stored in the database along with the user identification.

3.Biii Data Collection

Each user in Medidata Rave® is granted specific rights within the system, limiting the data that they can view or edit and the particular functions that they can perform. Data consistency checks may be performed prior to data submission to ensure that the proper type of data is submitted in the field (e.g., alphabetic vs. numeric, number of significant digits, etc.). Once data are submitted, an audit trail independently records the user ID, date and time of the entry and reason for change. Any actions that create, modify, or delete an electronic record are recorded. The audit trail is incremental and cannot be modified by any user.

The Medidata Rave® System performs edit checks on submitted data and notifies users with the results of these checks. In both cases, the user will be presented with a description of the discrepancy, and will be expected to address the problem. As with paper CRFs, the investigator is expected to review eCRF data on an ongoing basis.

To ensure the quality of clinical data across all subjects and sites, a clinical data management review will be performed on subject data received at the sponsor/designee. During this review, subject data will be checked for consistency, omissions, and any apparent discrepancies. In addition, the data will be reviewed for adherence to the protocol and regulatory standards. To resolve any questions arising from the clinical data management review process, data queries and/or site notifications will be created in the EDC system database for site resolution and closed by the sponsor/designee reviewer.

3.B.iv Data Access

During the conduct of the study, each investigative site can access all of its entered data, including complete audit information, through the Medidata Rave® System using a standard web browser. At the completion of the study, each investigator will be required to sign an EDC memo attesting to the completeness and accuracy of the data for each subject at his/her site. Also, each site will receive an archival copy on compact disc (CD) of the eCRFs,

representing all data entered for its subjects, in Adobe Acrobat (PDF) format. The CDs can be accessed, search, and copied.

4 Trial Documents and Records Retention

The investigator and designated staff are responsible for maintaining a comprehensive and centralized filing system of all study-related (essential) documentation, suitable for inspection at any time by representatives from the sponsor and/or applicable regulatory authorities. Elements include but are not limited to: the protocol with all amendments; Investigator's Brochure with all amendments; subject files containing completed eCRFs, original source documentation and informed consents; correspondence to and from the sponsor, health authorities and IRB; investigator's curricula vitae, license and financial disclosure; study monitor logs and reports; laboratory reference ranges and laboratory certifications; and pharmacy information pertaining to the accountability, handling and storage of the investigational product(s).

Subject files and other source data must be kept for the maximum period of time permitted by the hospital, institution or private practice, or as specified below. The study monitor must be consulted if the investigator wishes to assign the files to someone else, remove them to another location or is unable to retain them for the specified period.

The investigator must retain trial records for the amount of time specified by applicable laws and regulations. At a minimum, trial records must be retained for the amount of time specified by the Code of Federal Regulations, Title 21, Volume 5, which state that an investigator shall retain records required to be maintained under this part for a period of 2 years following the date a marketing application is approved for the drug for the indication for which it is being investigated; or, if no application is to be filed or if the application is not approved for such indication, until 2 years after the investigation is discontinued and FDA is notified. All trial documents shall be made available if required by relevant health authorities. The investigator should consult with the study monitor prior to discarding trial and/or subject files.

Sponsor will retain all sponsor-required documentation pertaining to the trial for the lifetime of the product. Archived data may be held on microfiche or electronic record, provided that a back-up exists and that a paper copy can be obtained from it, if required.

The sponsor will post trial information, including the results, on public registries in which the sponsor participates (e.g., clinicaltrials.gov, a service of the United States National Institutes of Health). The information on public registries may be transferred to other countries, as appropriate, for the uses described above. No subjects will be identified in this information.

5 FDA Financial Disclosure Requirement

In connection with the clinical study described in the protocol, the investigator certifies that, if asked, the investigator will read and answer the Clinical Investigator Financial Disclosure Form truthfully and to the best of investigator's ability. Investigator also certifies that, if asked, the investigator will have any other applicable party(s) (e.g., sub-investigators) read and answer the Clinical Investigator Financial Disclosure Form as a condition of their participation in the

study.

If the financial interests reported on the Clinical Investigator Financial Disclosure Form change during the course of the study or within one year after the last subject has completed the study as specified in the protocol, the investigator and the other applicable party(s) are obligated to inform the sponsor of such financial change.

6 Investigator Information

The investigator agrees that the sponsor may store, in an electronic database, for sponsor's ongoing and future processing and use, including for purposes of monitoring the conduct of this study and considering potential investigators for future studies, both administrative and qualitative information, including personal data (e.g., name, address, curriculum vitae, etc.), relating to the investigator's conduct of the study. The investigator further agrees that such information may be provided to FDA and/or other appropriate regulatory authority, consistent with sponsor's obligations to same. The investigator also agrees that the sponsor may post certain information concerning the investigator's participation in the study (e.g., study site phone contact information and study site location) on public registries in which the sponsor participates (e.g., clinicaltrials.gov, a service of the United States National Institutes of Health). The information on public registries may be used to contact the investigator by prospective study subjects or referring physicians. The information on public registries may be transferred to other countries, as appropriate, for the uses described above.

**APPENDIX E: CONFIDENTIALITY AND SECURITY OF PHARMACOGENOMICS
RESEARCH**

Confidential Subject Information for Pharmacogenomics Study

All information in this trial will be treated as confidential. The whole blood sample from randomized research subjects who have provided separate informed consent will be collected and sent to the sponsor (Tufts Center for Hemostasis and Thrombosis Research) for pharmacogenomics analysis. The sample will be labeled by the clinical site with the subject's unique study identification number, the sample type code (i.e., PG), study time point and the date/time of collection. A corresponding eCRF will be entered by the clinical site and will contain certain standard subject identifiers that are normally collected in the course of this clinical trial, such as subject initials, subject study identification number, and date of birth. This will enable authorized study sponsor personnel to accurately track the collection, storage and processing of the blood sample.

The sponsor, Tufts Center for Hemostasis and Thrombosis Research, will perform the DNA and RNA purification/extraction procedures and the subsequent genetic analysis utilizing the whole blood sample and derivative specimens (i.e., DNA and RNA). Upon receipt of the whole blood sample, the sponsor's designated staff will enter the subject study identification number into a coded data base and assign a new identifier (genetic sample code) to each sample. This new identifier will be linked to the subject study identification number assigned to the subject. From that point on, the whole blood sample, its derivative specimens and any results from the genetic analysis will be labeled with the same genetic sample code for each subject. The genetic sample code or "key" will be stored separately from the subject's eCRF and from the data resulting from the genetic analysis. This "key" will be maintained by the sponsor's designated staff. The underlying clinical trial database for the study will be stored by the unique subject study identification number within the electronic data capture (EDC) system (i.e., Medidata Rave[®]) maintained by the sponsor and sponsor's designee, RTI, International. The genetic research laboratory database will be stored according to the genetic sample code in a separate file (i.e., Microsoft Excel[®] spreadsheet) maintained by the sponsor. The sponsor will request certain clinical variables and outcomes collected during the entire course of the subject's participation in the underlying trial (i.e., up to 90 days following study drug administration) from RTI at the time of data analysis. The secure "key" will be used to match the genetic sample code to the original subject identification number to allow the sponsor to correlate the clinical variables and outcomes information collected during the course of the study (identified by unique subject identification number) with the information obtained from the genetic analysis (identified only by genetic sample code). The genetic research laboratory data will not be merged into the main clinical trial database and the personal identifying information from the clinical trial database will not be sent to the sponsor by RTI. The "key" could potentially be utilized to reconstruct the link between genetic information and identifiable clinical information, under other specific circumstances- verification of data accuracy, request for sample/specimen(s) destruction by the investigator on behalf of the subject or as mandated by regulatory authorities.

The "key" will be destroyed at the conclusion of the pharmacogenomics study, after the clinical information has been associated with the subjects' genetic sample code. Once this "key" is destroyed, the sample/specimen(s) and associated data derived from the genetic analyses of these sample/specimen(s) will be rendered anonymous and it will be impossible to identify any

specific individual subject's sample/specimen(s) and/or associated data.

Genetic analysis utilizing the DNA and RNA sample/specimen(s) will be performed by the sponsor and may be performed at one of the participating clinical trial sites designated by the sponsor if expertise in a particular genetic/genetic expression test is indicated. The pharmacogenomics sample/specimen(s) will not be used by investigators other than those conducting the original research protocol (main study), and will not be subjected to testing outside the stated purpose and objectives of the original research protocol (See **Section 6.7.3.1**), and will not be disseminated to other researchers who are not part of the original protocol. If applicable, sample/specimen(s) shipped by the sponsor to a clinical trial site will be identified only by the genetic sample code. If required for analysis, the sponsor may provide the clinical trial site with the clinical trial data set identified only by the genetic sample code. The clinical trial site will not have access to the "key" to link the genetic sample code to the individual's identifiers. Any sample/specimen(s) remaining with the clinical trial site after the genetic analysis has been performed will be returned to the sponsor or destroyed.

The informed consent form will be kept under secure storage at the clinical site for regulatory purposes and cannot be traced to any samples, test results, or medical information once the specimens have been rendered anonymous. Laboratory personnel performing the genetic testing will not have access to the informed consent document or the clinical trial database, nor will they be able to identify subjects from the coded sample/specimen(s). Sample/Specimen(s) will be identified to the laboratory staff only by the genetic sample code. Subjects who decline to sign the informed consent for the optional pharmacogenomics study will not have the whole blood sample collected, nor will they be excluded from participating in the underlying clinical trial.

Withdrawal from Pharmacogenomics Study

